6.4 Subject Withdrawal

This is a real-world study, and the study participation is completely voluntary. Subjects may withdraw voluntarily from the study at any juncture during the study observation period following the enrollment, for any reason. Site Investigator may terminate a Subject's participation in the study at any juncture, in specific scenarios, as outlined below.

6.4.1 Reasons for Withdrawal

Subjects are free to withdraw from participation in the study at any time upon request.

A Site Investigator may terminate a study Subject's participation in the study if:

- Any medical condition, event or situation occurs such that continued participation in the study would not be in the best interest of the Subject. This may include pregnancy among female Subjects, per clinician judgment.
- The Subject meets a study exclusion criterion (either newly developed or not previously recognized) that precludes further study participation.
- The Site Investigator or the study coordinator is unable to reach the Subject and the Subject is considered as lost to follow-up.

6.4.2 *Handling of Subject Withdrawals*

If a Subject requests withdrawal from the study voluntarily for any reason, the Site Investigators or site coordinator will follow-up with the patient to solicit and document the reason for withdrawal, unless the Subject is considered as lost to follow-up. If the Site Investigator determines that the withdrawal is related to an adverse drug reaction (ADR) or serious adverse event (SAE) associated with tirbanibulin, he/she will gather necessary information concerning the ADR/SAE. The Site Investigator may follow-up with the subject subsequently to ensure resolution of ADR/SAE episode and close out the study documentation for the concerned Subject. There will be no replacement of Subjects who withdraw or discontinue early from the study.

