6.2 Subject Exclusion Criteria

An individual who meets any of the following criteria will be excluded from participation in this study:

- Patients with any dermatological condition of the face or scalp that could interfere with the clinical evaluations.
- Hypertrophic AK lesions, open wounds or suspected skin cancers within close proximity of the treatment area.
- Anticipated need for in-patient hospitalization or in-patient surgery within the next 2 months.
- Patients unable to comply with the requirements of the study or patients who in the opinion of the study physician should not participate in the study.
- Patients for whom medical chart is inaccessible to physicians to complete baseline data collection.

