7.6 Early Termination Encounter (Study Encounter # x)

Site Investigators will attempt to follow the progress of every subject admitted to the study through to study completion. If a subject fails to complete requested study procedures (i.e, completion of online surveys, or complete study visits), a reasonable effort will be made to contact the subject and ascertain the reason(s) for non-compliance with study procedures.

If a subject does not complete the study for any reason (including Site Investigator discretion), the reason and circumstances for the subject's early termination will be documented; if possible, the assessments specified for the forthcoming (next) study encounter will be performed.

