12.3 General Statistical Procedures

12.3.1 Overview

Data from Site Investigators and study Subjects will be combined into one dataset. No site-specific analyses will be conducted. Validated instruments will be scored according to developer guidelines, reporting domain scores and overall summary scores, as appropriate. EPQ and other ad hoc questions will be analyzed and reported individually, based on the respective response scales. For all outcome measures, the analyses will focus on baseline, Week-8 and Week-24, as applicable.

All statistical analyses will be based on all available data assuming that all missing data are uninformative and will be conducted using appropriate statistical software, such as SAS. An interim analysis will be conducted after the completion of 8 weeks of data collection for all study

Subjects. The final study analyses will be conducted after the completion of 24 weeks of data collection for all study Subjects.

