7 DATA TABLES

All patients who received at least one dose of tirbanibulin during the study observation period and had at least some data pertaining to study primary endpoints (PROs) at Week 8 will be included in **Full Analysis Set (FAS)** to facilitate the planned descriptive analysis.

Correspondingly, patients who completed the study survey at Week 8 will be included in FAS, since patients answering Week 8 survey will have completed all relevant PRO related questions.

Safety data analyses will be conducted among the **Safety Population**, that correspond to the entire study cohort that took at least one dose of tirbanibulin. Correspondingly, all patients completing the baseline survey and took at least one dose of tirbanibulin, amounting to N=300 will be included in this analysis.

Section 7.1 Patient Demographics, Perceptions & PROs (FAS Population)

Table 1.1 Population	25
Table 1.2 Patient Demographic Characteristics	26
Table 1.3 Patient Self-Assessment: AK Treatment Motivators.....	28
Table 1.4 Patient Self-Assessment: Baseline Skin Texture.....	28
Table 1.5 Patient Reported Medication Compliance.....	29
Table 1.6 SKINDEX-16: Patient Response Summary.....	30
Table 1.7 SKINDEX-16: CFB at Week-8 for Individual Items.....	36
Table 1.8 SKINDEX-16: Domain Scores.....	41
Table 1.9 Subgroup Analysis of SKINDEX-16 Domain Scores.....	42
Table 1.10 Patient Evaluation of Overall Appearance in the Original Treated Area.....	43
Table 1.11 Subgroup Analysis of Patient Evaluation of Overall Appearance in the Original Treated Area	44
Table 1.12 Treatment Satisfaction Questionnaire for Medication (TSQM-9): Patient Scores in the Original Treated Area.....	46
Table 1.13 Subgroup Analysis of TSQM-9 Patient Domain Scores	47
Table 1.14 Patient Satisfaction with Tirbanibulin in the Original Treated Area (looks/texture)	48
Table 1.15 Subgroup Analysis of Patient Satisfaction with Treatment Ability to Improve How Skin Looks in the Original Treated Area	49
Table 1.16 Subgroup Analysis of Patient Satisfaction with Treatment Ability to Improve Skin Texture in the Original Treated Area ..	51
Table 1.17 Patient Relative Satisfaction of Tirbanibulin in Comparison with Other Topical Medications for AK in the Original Treated Area	53
Table 1.18 Subgroup Analysis of Patient Relative Satisfaction of Tirbanibulin, Regarding Duration of Skin Reactions	56
Table 1.19 Subgroup Analysis of Patient Relative Satisfaction of Tirbanibulin, Regarding Severity of Skin Reactions	58

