3 /4 Minimally/ Not Cleared	n (%)	n (%)

Table 2.11 IGA Success at Week 8 in the Original Treated Area

Character	Week 8
IGA Success	N=x
No	n (%)
Yes	n (%)

Note: IGA success at Week 8, defined as an IGA score of completely cleared (0) or partially cleared (1) in AK status in the original treated area at Week 8. The denominator for the percentages is the number of patients with available data (N=XX). X patients had missing data at Week 8.

Table 2.12 Subgroup Analysis of IGA Success

% IGA Success (Completely/Partially Cleared)		Week 8 n (%)	Week 24 n (%)
Subgroups			
Gender			
Male			
Female			
p -value			
Age Group			
≤ 49 years			
50 – 64 Years			
≥ 65 years			
p -value			
AK Treatment Location			
Face			
Scalp			
Both			
p -value			
Fitzpatrick Skin Type			
I / II			
III / IV / V / VI			
p -value			
Skin Photodamage			
Absent/mild			
Moderate/Severe			
p -value			
History of Skin Cancer			
Yes			
No			
p -value			
Prior Treatment Experience: Use of Cryosurgery			
Yes			
No			
p -value			
Prior Treatment Experience: Use of Other Topical Treatments			
Yes			
No			
p -value			

Prior Treatment Experience: Treatment Naïve at Baseline

Yes

No

p-value

P-values correspond to difference between strata within respective time periods.

Table 2.13 Clinician Evaluation of Overall Appearance in the Original Treated Area

Character	Week 8 (N=x)	Week 24 (N=X)
Compared to 8 / 24 weeks ago, how has the patient's overall appearance of the skin in the original AK treated area changed?		
1. Much Worse	AK8_2	AK8_2
2. Somewhat Worse	n (%)	n (%)
3. No Change	n (%)	n (%)
4. Somewhat improved	n (%)	n (%)
5. Much Improved	n (%)	n (%)
(1/2) Much/Somewhat Worse	n (%)	n (%)
(3) No Change	n (%)	n (%)
(4/5) Somewhat/Much Improved	n (%)	n (%)

Table 2.14 Subgroup Analysis of Clinician Evaluation of Overall Appearance in the Original Treated Area

% Somewhat / Much Improved	Week 8 n (%)	Week 24 n (%)
Subgroups		
Gender		
Male		
Female		
p -value		
Age Group		
≤ 49 years		
50 – 64 Years		
≥ 65 years		
p -value		
AK Treatment Location		
Face		
Scalp		
Both		
p -value		
Fitzpatrick Skin Type		
I / II		
III / IV / V / VI		
p -value		
Skin Photodamage		
Absent/mild		
Moderate/Severe		
p -value		
History of Skin Cancer		
Yes		
No		
p -value		
Prior Treatment Experience: Use of Cryosurgery		
Yes		
No		
p -value		
Prior Treatment Experience: Use of Other Topical Treatments		
Yes		
No		

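### Ending participation for a newly developed exclusion criterion can drop poor outcomes from the Week 8 IGA and Skindex-16 results

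*Protocol*

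**What the plan says.** Protocol 6.4.1 introduces its grounds with "A Site Investigator may terminate a study Subject's participation in the study if", and the second ground is "The Subject meets a study exclusion criterion (either newly developed or not previously recognized) that precludes further study participation". Protocol 6.2 has a criterion on local lesions, "Hypertrophic AK lesions, open wounds or suspected skin cancers within close proximity of the treatment area". A separate one looks ahead to hospital care: "Anticipated need for in-patient hospitalization or in-patient surgery within the next 2 months". A further one covers skin disease at either site that might disturb the assessments.

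For a Subject who stops early, Protocol 7.6 says that "if possible, the assessments specified for the forthcoming (next) study encounter will be performed". Neither document says whether a reading taken then counts as the Week 8 reading.

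On analysis, SAP section 7 states that "patients who completed the study survey at Week 8 will be included in FAS". The note to SAP Table 2.11 (IGA success) reads "The denominator for the percentages is the number of patients with available data (N=XX). X patients had missing data at Week 8". SAP 6.7 plans no imputation. Protocol 12.3.1, repeated in SAP 6.3.1, makes all analyses "based on all available data assuming that all missing data are uninformative".

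Protocol 12.8 plans to compare completers with discontinuers and to describe reasons for missing data and time to drop-out. SAP 6.9 keeps only a missing-data analysis that depends on an unusual amount being missing, with no threshold. The one sensitivity table in SAP 7.5 stratifies IGA by visit type.

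**The concern.** Treatment lasts 5 days and follow-up runs to Week 24. For almost all of that time, ending participation withdraws no drug; it stops data collection. Some conditions that justify exclusion at baseline carry information about outcome once the Subject has been dosed. A new open wound may be a reaction: Protocol 8.5.1 lists erosion/ulceration among the LSRs. New hypertrophic AK or a suspected skin cancer beside the treated area may go with a poor result. An interfering skin condition may itself be a reaction.

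If such Subjects are terminated before Week 8 and not assessed, loss depends on outcome, and the assumption that missing data are uninformative is hard to defend for them. At stake are the primary endpoint (Skindex-16 at Week 8), the secondary endpoint (IGA success at Week 8) and the satisfaction scores, all of which could look better than they should.

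**Working it through.** **Step 1: follow one Subject through the plan.** A dosed Subject develops a suspected skin cancer near the treatment area at Week 4, and the site ends participation.

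- *Effectiveness and PROs.* With no Week 8 survey, the Subject is outside the FAS of SAP section 7, so no Skindex-16 or TSQM-9 score is used. With no Week 8 IGA, the Subject is outside the denominator of Table 2.11. Nothing is imputed. An early-termination assessment might fill the gap, but it is taken only where possible and has no stated place in the Week 8 tables.
- *Safety.* The Subject stays in the Safety Population, which requires only one dose (SAP 6.2). AEs already recorded remain. SAEs are reported even when they lead to withdrawal, and are followed to resolution or stabilisation (Protocol 8.5.2). What can be lost is an event after termination, or an LSR never entered on a Week 8 or early-termination form. Table 4.13 is organised by visit, and Appendix A collects early-termination items only if relevant.
- *Disposition.* Tables 4.11 and 4.12 have no row for this reason. It would most likely fall under the residual clinician-decision category, so its frequency would not be visible.

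**Step 2: size for IGA success.** The documents give no expected success rate, termination rate or dropout rate, and the sample of about 300 is a feasibility figure. There is no planned figure to reproduce. The following is an illustration.

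Inputs: N = 300 (both documents); true success p of 60%, 70% or 80% (assumed), so S = 180, 210 or 240; k Subjects terminated (assumed), all of them failures with no usable Week 8 rating (worst case).

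Reported success = S / (N − k).

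| Terminated, k | p = 60% | p = 70% | p = 80% | Upward shift, points |
|---|---|---|---|---|
| 1%, 3 | 180/297 = 60.6% | 210/297 = 70.7% | 240/297 = 80.8% | 0.6 to 0.8 |
| 2%, 6 | 180/294 = 61.2% | 210/294 = 71.4% | 240/294 = 81.6% | 1.2 to 1.6 |
| 5%, 15 | 180/285 = 63.2% | 210/285 = 73.7% | 240/285 = 84.2% | 3.2 to 4.2 |
| 10%, 30 | 180/270 = 66.7% | 210/270 = 77.8% | 240/270 = 88.9% | 6.7 to 8.9 |

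For scale, the 95% half-width at n = 300 is 1.96 × √(p(1 − p)/300), or 5.5, 5.2 and 4.5 points for p = 60%, 70% and 80%. At 70%, terminating 2% shifts the result by 1.4 points, about 0.28 of the half-width; 5% shifts it by 3.7 points, about 0.71; and 10% shifts it by 7.8 points, about 1.5.

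If a share r of the terminated Subjects were in fact successes, reported success would be (S − rk)/(N − k), and the shift would vanish at r = p. The table is therefore an upper bound for each k under the assumption that no terminated Subject does worse than failure on a binary endpoint.

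No comparable figure can be given for Skindex-16, because the documents state no expected mean or SD. Only the direction can be argued.

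**The case against.** A reader might infer that the exclusion criteria are re-applied through follow-up. The documents do not support that. The rule is permissive, it is limited to criteria that preclude further participation, and Appendix A schedules selection criteria at baseline only.

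A reader might also infer that harms are removed from the results. That is contradicted by the Safety Population, by AE and SAE recording, by the information gathered on withdrawals related to an ADR or SAE (Protocol 6.4.2), and by Table 4.11, which counts terminations against 300 at each visit. Only the narrow gap in Step 1 remains.

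Equating the criteria with treatment failure is partly inference. Nothing says that an expected erosion is an open wound in the sense of 6.2. The lesion criterion concerns the neighbourhood of the treatment area, whereas the IGA rates the treated area itself. An anticipated hospital stay says nothing about AK clearance, and pre-planned treatment of an unrelated, unworsened condition is outside the SAE definition. These objections stand, and they rule out scoring a nearby lesion as IGA failure.

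It is also fair to say that the completer FAS and available-data denominator affect every dropout, and that deleting this one ground would leave the best-interest ground of 6.4.1, under which the same Subjects could be terminated. That stands too, and it shapes the fix. It does not remove the problem: an outcome-related ground for ending data collection, joined to an analysis that omits those without data, allows selective loss. The number missing will be shown in Table 2.11, but not why they are missing.

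**Conclusion.** The point holds in limited form. Site termination for a newly developed exclusion criterion can remove poor outcomes from the Week 8 IGA and Skindex-16 results and so can bias them in favour of tirbanibulin. Bias is possible rather than certain: it needs terminations before Week 8, among Subjects doing worse than average, without a usable assessment. In the worst case at 70% true success, the reported rate rises to between 70.7% (1% terminated) and 77.8% (10% terminated). At 1% to 2% the shift is well inside the sampling error. The success and termination rates are assumptions. The plan as written would not show how often this reason occurs, and the SAP has dropped the comparison that would help judge its effect.

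**What to change.** 1. **Protocol 6.4.1.** Remove new development of a criterion as a ground for ending data collection. State that Subjects terminated by the site after first dose, under any ground, continue Week 8 and Week 24 data collection unless they withdraw consent or cannot be reached. Clinical care stays with the investigator.
2. **SAP 6.5 and 6.9.** Beside Table 2.11, add IGA success over all dosed Subjects, with a missing Week 8 IGA counted as non-success. In the illustration this returns 210/300 = 70%. In practice it is a conservative companion figure, since some Subjects lost for other reasons will have cleared. Say in the same place whether an early-termination IGA outside the Week 8 window counts.
3. **SAP 6.9 and Tables 4.11 and 4.12.** Restore the completer versus discontinuer comparison from Protocol 12.8, and give this termination reason its own row.

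The cost is a short amendment, one disposition code and a little more analysis. No visit is added to the schedule. The IGA figure may be less favourable.

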7 STUDY SCHEDULE & PROCEDURES

Study eligible patients who are considered as candidates for tirbanibulin treatment as part of usual care AK management will be screened, consented, and recruited into the study, followed for up to 24 weeks post-index date, encompassing three distinct data collection encounters. With 'T' being the index date of tirbanibulin treatment initiation, the baseline data collection (from both Site Investigators and Subjects) may transpire anytime between $T = -2$ weeks post-index date and $T = +7$ days post-index date; the 8-week follow-up data collection (Study Encounter # 2; from both Site Investigators and Subjects) will happen at $T = 8$ weeks post-index date ± 7 days; and 24-week follow-up data collection (Study Encounter #3; from both Site Investigators and Subjects) will happen at $T = 24$ weeks post-index date ± 14 days. Index date is the planned date of first application/initiation of tirbanibulin treatment, after the subject was prescribed the tirbanibulin.

Different data elements will be collected from Site Investigators and from study Subjects at these data collection encounters, as outlined below.

The schedule of events is summarized in Appendix A.

7.1 First Study Encounter / Baseline

Baseline data collection will take place at the time of subject enrollment into the study or within a few days of recruitment. The subject encounters are expected to take place during in-person subject visits to the clinic. The recruited Site Investigators and study Subjects will be sent a weblink to the eDCFs and survey respectively for their completion. Subjects will be able to access the surveys on their mobile phone, using a study-specific Mobile App.

The following data elements will be collected at baseline, from patient medical charts and/or per Site Investigator's best clinical judgement based on their recent encounter with the study subject while prescribing tirbanibulin as part of usual care and based on subject's recent past medical history:

- Demographics (e.g., age, gender).
- General clinical characteristics, as documented in medical charts (incl. blood pressure, waist circumference, height/weight measurements, comorbidities).
- AK disease characteristics (incl. AK history, IGA of severity of current skin photodamage in the AK treated area on the face or scalp (using EPQ item)).
- Past AK treatment history (used ever, and those used within the past 6 months).
- Tirbanibulin treatment characteristics (dose, frequency, date of recommendation).
- Concomitant medications (for AK and comorbidities).

The following data elements will be collected at baseline, from study Subjects, via online survey portal or a mobile app:

- Demographics (e.g., gender, race/ethnicity, education, employment/school status, living status).
- Perceptions of AK-related symptoms and impact of AK on Subject QoL, incl. emotional well-being and functioning, using Skindex-16.

7.2 Shipment of Study medication

Following the Site Investigator's decision to prescribe tirbanibulin (Klisyri®) to study eligible patients, a commercial supply of the appropriate dose and quantity of study medication will be shipped to the attention of Site Investigator at their clinic/site. The Site Investigators will be asked to record the planned first day of administration of tirbanibulin, and this date will constitute the study 'index date', upon which the follow-up encounter timepoints (at weeks 8 & 24) will be determined.

7.3 Second Study Encounter

At the completion of 8 weeks (\pm 7 days) post-index date, the Site Investigators and Subjects will be asked to complete the data collection corresponding to the study primary endpoints. The subject encounters (post-baseline) are expected to take place during in-person subject visits to the clinic, but remote/virtual visits may be allowed where COVID-related protocols prevent in-person visits.

The Site Investigators will complete the following, based on the information documented in the corresponding patient medical charts, and per Subject interaction and per clinical judgment guided by observing study Subject via in-person or remote/virtual visit:

- IGA of AK status (in relation to baseline), and current severity of skin photodamage in the AK treated area on the face or scalp (using EPQ item).
- Investigator rating of overall appearance of the AK treated area (using EPQ item).
- Modifications to tirbanibulin treatment characteristics following the initial prescription, if applicable.
- Perceptions and satisfaction with different attributes of tirbanibulin, and future preference to re-treat with tirbanibulin (using ad hoc and EPQ items).
- Any unplanned patient encounters in the past 8 weeks.
- Newly documented changes to patient clinical characteristics (incl. comorbidities and concomitant medications), as documented in medical charts in past 8 weeks since the baseline encounter.

- AEs, ADRs and LSRs observed in the past 8 weeks, as documented in the medical charts.
- Information on withdrawal from study (if occurred within the past 8 weeks).

The study Subjects will provide the following information via online survey portal or a mobile app:

- Perceptions of AK-related symptoms and impact of AK on Subject QoL, incl. emotional well-being and functioning, using Skindex-16.
- Self-rating of overall appearance of the AK treated area (using EPQ item).
- Perceptions and satisfaction with different attributes of tirbanibulin (using TSQM-9 and EPQ items, where applicable), and future preference to re-treat with tirbanibulin.

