3.2 Key Study End Points

The primary endpoint of the study will be the PROs, in terms of self-perceived AK symptoms and impact of AK on emotional well-being and functioning as measured using Skindex-16, at Week 8.

The secondary endpoint will be the proportion of Subjects with IGA success, defined as an IGA score of completely cleared (0) or partially cleared (1) in AK status in the treated area at Week 8.

Additional endpoints of the study will include (not exclusively):

- At Week 8, Mean satisfaction scores on TSQM-9 (effectiveness, convenience and overall satisfaction) as well as ad hoc satisfaction questions.
- At Week 8, Mean satisfaction scores on ad hoc physician satisfaction questionnaire.
- At Week 8, proportion of Subjects and Investigators rating the overall appearance of the AK treated area as ‘somewhat improved or much improved.’
- At Week 8, proportion of Subjects and Investigators reporting ‘somewhat likely or very likely’ to consider tirbanibulin in the future to retreat their AK.
- Frequency of documented adverse events (AEs), serious adverse events (SAEs) and LSRs during the first 8-weeks of the study observation period.
- Investigator rating of severity of skin photodamage at Weeks 8 and 24.
- Among Subjects with prior topical treatment experience at baseline:
 - At Week 8, proportion of Subjects and Investigators respectively rating ‘convenience/ease of use’ of tirbanibulin, and ‘overall satisfaction’ with tirbanibulin as ‘somewhat better or much better’ in comparison to previous topical treatments to treat their AK.
 - At Week 8, proportion of Subjects and Investigators respectively rating ‘duration of skin reactions’, ‘severity of skin reactions’ and ‘impact on daily activities due to skin reactions’ related to tirbanibulin, as ‘somewhat better or much better’ in comparison to previous topical treatments to treat their AK.

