7.5 AK Photography & Subject Insights

In a small subset of sites (up to 2), Site Investigators will utilize Canfield® photography equipment to take photographs of Subject's AK treated area in the face or scalp to visually capture the clinical status of AK at baseline (study entry) and at Weeks 1, 2, 4 and 8, and will document their assessment/grading of LSR. In addition to the baseline and Week-8 encounters, Subjects at these sites will hence be consented to undertake additional in-person visits at Weeks 1, 2 & 4. At Week 8, the Subjects from these sites will also be asked to record a 1-3 minute audio narrating their perceptions of treatment benefits associated with the tirbanibulin.

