9 CANFIELD PHOTOS OF AK PATIENTS FROM SITE AK01

A separate file will be attached, summarizing the canfield photos of AK patients from Site # AK01.

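### LSRs are captured by Week 8 look-back at most sites but graded at Weeks 1, 2 and 4 at up to two, and the SAP does not say how the early grades are used

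*Protocol*

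**What the plan says.** Among the additional endpoints, Protocol 3.2 and SAP 2.2 name "Frequency of documented adverse events (AEs), serious adverse events (SAEs) and LSRs during the first 8-weeks of the study observation period".

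For all sites, Protocol 7.3 lists among the Week 8 investigator items "AEs, ADRs and LSRs observed in the past 8 weeks, as documented in the medical charts". The sentence introducing that list says the form is completed from the charts "and per Subject interaction and per clinical judgment guided by observing study Subject via in-person or remote/virtual visit". The schedule of events (Appendix A in both documents) has no encounter between baseline and Week 8, and the treatment course lasts 5 days (Protocol Summary).

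Protocol 7.5 sets up a different process at a few sites: "In a small subset of sites (up to 2), Site Investigators will utilize Canfield® photography equipment". Their investigators photograph the treated area at baseline and "at Weeks 1, 2, 4 and 8, and will document their assessment/grading of LSR", and "Subjects at these sites will hence be consented to undertake additional in-person visits at Weeks 1, 2 & 4".

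SAP 6.3.1 combines all data into one dataset and rules out site-specific analyses. SAP 6.6.9 reports LSR frequency in the Safety Population. Table 4.13 shows LSR grade at Baseline, Week 8 and Week 24, and Table 4.14 lists LSRs by patient with timepoint, grade and onset date. For the photography, SAP section 9 says only: "A separate file will be attached, summarizing the canfield photos of AK patients from Site # AK01".

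**The concern.** The same endpoint is ascertained in two ways. Most subjects have no scheduled assessment between a 5-day course and Week 8, so a reaction that has resolved by then is counted only if it was charted earlier, or recalled and recorded at the visit. Photo-site subjects are examined and graded three times in that interval. One frequency across both groups depends partly on how reactions were looked for, and a reader of Table 4.13 cannot see this. For the six graded reactions the table has rows only for mild, moderate and severe, so a subject examined and found clear cannot be told from one whose reaction was never recorded.

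Safety and tolerability is a study objective, and Protocol 2.1 presents less severe LSRs as an advantage of the product. An undercount would therefore lean in the favourable direction. Meanwhile the only scheduled early grading in the study has no planned summary.

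**Working it through.** The plan states no expected LSR rate, so there is no figure to reproduce.

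**Inputs from the documents**
- Planned subjects: 300, from at most 50 sites (Protocol 6).
- Maximum subjects per site: 25 (Protocol 6.3.2).
- Photo sites: up to 2 (Protocol 7.5, SAP 5.3.5), but only AK01 in SAP section 9.
- Treatment: 5 days; next scheduled encounter at Week 8 (Appendix A).

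**Step 1: what happens to the early grades.** No sentence in either document settles this. If the Week 1, 2 and 4 grades feed Table 4.13, that table mixes two ascertainment methods without saying so. If they do not, the scheduled early grading is left to a possible place in the Table 4.14 listing and a photo file. Both cannot be true together, and either one needs a stated rule.

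**Step 2: share of subjects actively graded.**
- Two sites at the cap: 2 × 25 / 300 = 50/300 = 16.7%.
- One site at the cap: 25/300 = 8.3%.
- Average site size if all 50 sites are used: 300/50 = 6, giving 12/300 = 4% for two sites and 6/300 = 2% for one.

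So 83.3% to 98% of subjects have no scheduled LSR assessment between baseline and Week 8. For them the look-back comes about 56 − 5 = 51 days after the course ends.

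**Step 3: illustrative size.** Let p be the true incidence, s the probability that an LSR is captured at non-photo sites, and f the actively graded share. Assume full capture of LSRs at photo sites and the same p everywhere. Then

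reported frequency = p × [f + (1 − f) × s]

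shortfall = p × (1 − f) × (1 − s)

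Neither p nor s is in the documents. With an assumed p = 70%:

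| s (assumed) | f = 50/300 | f = 25/300 | early grades not used (f = 0) |
|---|---|---|---|
| 0.25 | 26.2% | 21.9% | 17.5% |
| 0.50 | 40.8% | 37.9% | 35.0% |
| 0.75 | 55.4% | 54.0% | 52.5% |
| 1.00 | 70.0% | 70.0% | 70.0% |

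For example, 0.70 × [0.1667 + 0.8333 × 0.50] = 0.70 × 0.5833 = 40.8%, a shortfall of 29.2 points. With s = 0.50 and f = 50/300, p = 50% gives a shortfall of 20.8 points and p = 90% gives 37.5.

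**Step 4: which part matters.** Without the early grades the shortfall is p × (1 − s). Including them multiplies it by (1 − f), so they remove only the fraction f of it: at most one sixth, whatever p and s are. At p = 70% and s = 0.50 they raise the figure by 40.8 − 35.0 = 5.8 points (two sites at the cap) or 37.9 − 35.0 = 2.9 points (one). Combining the sites therefore moves the figure up, and only slightly. The remaining shortfall comes from capture at the other sites.

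**Step 5: precision of the graded subset.** At an assumed 70%, the 95% half-width is 1.96 × √(0.7 × 0.3 / n): ±12.7 points for n = 50 and ±18.0 points for n = 25, before any allowance for site effects.

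**The case against.** The strongest reply is that the endpoint is worded as the frequency of documented events, so the plan never claims to estimate incidence. That stands, and it limits the problem to how the table will be read: the title of Table 4.13 does not carry the qualifier. Absolute LSR severity is not part of that endpoint wording either.

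A reader might infer that an LSR is counted only if it was charted. The documents do not support this. The Week 8 lead-in allows subject interaction and clinical judgment, footnote 5 of Appendix A places LSR data among the investigator assessments, and Protocol 13 accepts direct eDCF entry as source data where no earlier record exists. The baseline window also runs to 7 days after the index date (Protocol 7), so some early reactions could be recorded at baseline. These routes narrow the gap, but away from the photo sites none is a scheduled examination during the weeks after treatment.

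A reader might also infer that the early grades are demonstrably pooled into Table 4.13, or that graded data have no table at all. Pooling is only an inference from the single dataset and the single Safety Population frequency. Grades are tabulated at Baseline, Week 8 and Week 24, and Table 4.14 could hold the earlier ones. What is missing is a rule for the Week 1, 2 and 4 grades and a summary of them.

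Finally, one or two sites chosen for photography, whose subjects agreed to extra visits, are a small and selected group. That stands, and it rules out treating them as the source of a definitive incidence.

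**Conclusion.** The point holds as a gap in ascertainment and reporting for an additional endpoint. Sites differ in how LSRs are found, the SAP does not say whether the Week 1, 2 and 4 grades count, and no table summarises them or separates the photo sites. Table 4.13 may understate incidence. That direction is reasonable for reactions to a 5-day course that may resolve before Week 8, but it is not shown by the documents.

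The size is unknown. The illustrative shortfalls at an assumed 70% incidence run from zero with complete capture to 52.5 points with 25% capture and the early grades unused, and they rest entirely on assumed values. What does not depend on those values, given full capture at photo sites and equal incidence across sites, is that at least five sixths of any shortfall would remain after the photo-site grades are included. It would be wrong to conclude that pooling causes the understatement.

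**What to change.** 1. State in the SAP the source of LSR data at each type of site, and whether the Week 1, 2 and 4 grades enter Table 4.13.
2. Present Table 4.13 by ascertainment method, photo sites versus all other sites, and label the latter 'documented LSRs'.
3. Add a descriptive table for photo-site subjects: LSR grade at Weeks 1, 2, 4 and 8 and maximum grade, with n and 95% confidence intervals. Describe it as the actively assessed subset, not as the definitive incidence estimate.
4. Amend the exclusion of site-specific analyses (Protocol 12.3.1, SAP 6.3.1) to allow this. The SAP already accepts the principle: section 6.9 and Table 5.1 stratify IGA success by visit type, and sections 8 and 9 are devoted to one site.
5. Reconcile the up-to-two photo sites in Protocol 7.5 and SAP 5.3.5 with Site AK01 alone in SAP section 9.
6. Confirm where the Week 1, 2 and 4 grades are recorded. Neither schedule of events has a column for those visits, and neither document says that the grades reach the eDCF.

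The cost is one split and one extra table, with no added visits, provided the grades were recorded as Protocol 7.5 requires. The subset will be small and imprecise (about ±13 to ±18 points at an assumed 70%), and the LSR figure may look less favourable. Splitting the table does not recover reactions missed at the other sites; it only makes the limitation visible.
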